### **12.11.8 Safety Analyses**

Summaries and analysis of safety data will be presented for the Safety Analysis Population.

Solicited AEs will be summarized by severity for each day post third mRNA-1273 vaccination (Substudy Days 1-8) and as the maximum severity over all 8 days. Additionally, solicited AEs will be analyzed by taking the most severe response over the follow-up period and using standard techniques, such as exact confidence intervals (CI), to summarize the proportion of subjects reporting each symptom, any application site symptom, and any systemic symptom.

Unsolicited non-serious AEs will be collected from the time of the third mRNA-1273 vaccination through 28 days after the third mRNA-1273 vaccination. Unsolicited AEs will be coded by MedDRA for preferred term and system organ class (SOC). SAEs, Protocol Specified AESIs, MAAEs, and NOCMCs will be collected from the time of first mRNA-1273 vaccination through 12 months after the third mRNA-1273 vaccination. The numbers of SAEs and MAAEs will be reported by detailed listings showing the event description, MedDRA preferred term and SOC, relevant dates (vaccinations and AEs), severity, relatedness, and outcome for each event. Non-serious unsolicited AEs will be summarized as number and percentage of subjects reporting at least one event in each MedDRA preferred term and SOC, cross tabulated by severity and relationship to study product. Additionally, the proportion of subjects and exact 95% CIs of AEs in aggregate and by MedDRA categories will be computed.

Clinical laboratory data will be summarized by severity for each substudy visit, and as the maximum over all post-vaccination substudy visits. Graphical presentations may include box plots and shift plots.

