### 12.1 Overview

All subjects in this clinical trial were scheduled to receive two mRNA-1273 vaccinations, 28 days apart, at dosages of 25, 50, 100, or 250 mcg (see [Table 1](#)), with the last scheduled follow-up visit occurring at 365 days after the second vaccination (see [Table 4](#)). During the course of the main study, interim efficacy data from a Phase 3 placebo-controlled clinical trial of mRNA-1273 (COVE), administered as 2 doses of 100 mcg given 28 days apart, demonstrated vaccine efficacy of 94.1% (95% CI: 89.3%, 96.8%) for the prevention of symptomatic, confirmed COVID-19 (Baden, LR, et al. 2020). After review of the interim safety and efficacy data from that clinical trial, the FDA granted on December 18, 2020 an Emergency Use Authorization (EUA) for the mRNA-1273 vaccine in adults 18 years of age and older.

To potentially enhance and extend the duration of protection provided by the 2-dose vaccination schedule of mRNA-1273 administered in the main study, and to gain an understanding of the immune responses to a third dose of mRNA-1273, subjects in the main study may participate in an optional third mRNA-1273 vaccination substudy, detailed in [Section 12, Appendix A](#).

Substudy subjects will receive a third mRNA-1273 vaccination, administered via an IM injection at a dosage of 100 mcg/0.5 mL, given six to twelve months after receipt of their second vaccination in the main study. Substudy subjects will be followed for safety, reactogenicity, and immunogenicity endpoints through 12 months post third vaccination (Substudy Day 366).

To be eligible to participate in the substudy, subjects must have received both the first and second mRNA-1273 vaccinations in the main study. Other eligibility criteria are specified in [Appendix A](#). Subjects who received only one mRNA-1273 vaccination in the main study will be advised to receive an FDA authorized or approved COVID-19 vaccine, according to the recommended schedule, when available to them outside of this trial, unless they have a contraindication to COVID-19 vaccines that are available.

Subjects who elect not to participate in the optional third mRNA-1273 vaccination substudy or are not eligible for the substudy will continue to be followed according to the Schedule of Activities for the main study (see [Table 4](#)) with the Final Study Visit 14 occurring at Day 394 ( $\pm 14$  days).

Dosing for the optional third mRNA-1273 vaccination substudy is found in [Table 13](#).

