## 12.4 Objectives and Endpoints

**Table 12: Objectives and Endpoints (Outcome Measures)**

OBJECTIVES	ENDPOINTS (OUTCOME MEASURES)
Primary	

 
To evaluate the safety and reactogenicity of a third mRNA-1273 vaccination, at a dosage of 100 mcg.
 
	
 
Frequency and grade of each solicited local and systemic reactogenicity AE during a 7-day follow-up period post third mRNA-1273 vaccination.
 
Frequency and grade of any unsolicited AEs during the 28-day follow-up period post third mRNA-1273 vaccination.
 
Frequency of any SAEs, Protocol Specified AESIs, NOCMCs, and MAAEs from Substudy Day 1 to Substudy Day 366.
 

Secondary	

OBJECTIVES	ENDPOINTS (OUTCOME MEASURES)

 
To evaluate the immunogenicity as measured by IgG ELISA to the SARS-CoV-2 S (spike) protein following a third mRNA-1273 vaccination, at a dosage of 100 mcg, at all timepoints after the third mRNA-1273 vaccination.
 
	
 
GMT of antibody at each timepoint after the third mRNA-1273 vaccination.
 
Percentage of subjects who seroconverted, defined as a 4-fold change in antibody titer from the pre-third mRNA-1273 dose baseline (Substudy Day 1) at each post-vaccination timepoint and pre-first mRNA-1273 dose baseline (Main Study Day 1).
 
The GMFR in IgG titer from the pre-third mRNA-1273 dose baseline (Substudy Day 1) at each post-vaccination timepoint and pre-first mRNA-1273 dose baseline (Main Study Day 1).
 

Exploratory	

 
To evaluate the immunogenicity as measured by pseudovirus neutralization and other viral neutralization assays following a third mRNA-1273 vaccination, at a dosage of 100 mcg.
 
	
 
GMT of Neut antibody at each timepoint after the third mRNA-1273 vaccination.
 
Percentage of subjects who seroconverted, defined as a 4-fold change in Neut antibody titer from the pre-third mRNA-1273 dose baseline (Substudy Day 1) at each post-vaccination timepoint and pre-first mRNA-1273 dose baseline (Main Study Day 1).
 
The GMFR Neut antibody titer from the pre-third mRNA-1273 dose baseline (Substudy Day 1) at each post-vaccination timepoint and pre-first mRNA-1273 dose baseline (Main Study Day 1).
 

OBJECTIVES	ENDPOINTS (OUTCOME MEASURES)

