## 12.10 Adverse Events and Serious Adverse Events

### 12.10.1 Reporting of Adverse Events

Reporting of all AEs, solicited and unsolicited, will occur during the period from administration of the third mRNA-1273 vaccine on Substudy Day 1 through Substudy Day 29.

Solicited AEs (i.e., reactogenicity) will be collected using a memory aid and recorded on the appropriate DCF from the time of the third mRNA-1273 vaccination through 7 days post third mRNA-1273 vaccination (Substudy Days 1-8).

Unsolicited AEs of all severities will be reported from the time of the third mRNA-1273 vaccination on Substudy Day 1 through Substudy Day 29.

After Substudy Day 29 through the end of the substudy (Substudy Day 366), only SAEs, Protocol Specified AESIs, MAAEs, and NOCMCs will be reported as AEs.

SAEs, Protocol Specified AESIs, MAAEs, and NOCMCs will be collected from Substudy Day 1 through the end of the substudy (Substudy Day 366).

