### **12.11.3 Populations for Analyses**

The Safety Analysis population includes all subjects who received the third mRNA-1273 vaccination.

The modified intent-to-treat (mITT) population includes all subjects who received of the third mRNA-1273 vaccination and contributed both pre- and at least one post-third mRNA-1273 vaccination venous blood samples for immunogenicity testing for which valid results were reported.

In the final analysis, protocol deviations will be reviewed to determine which protocol deviations may affect the analysis. The per protocol (PP) population will then be defined – and this includes all subjects in the mITT subset with the following exclusions:

- Data from all available visits for subjects found to be ineligible at the time of the third mRNA-1273 vaccination.
- Data from all substudy visits subsequent for the protocol deviations that are considered to affect the science.
- Data from any substudy visit that occurs substantially out of window.

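### Appendix A gives two start points for SAEs, AESIs, MAAEs and NOCMCs, so the substudy's primary safety analysis could take in events from before the third dose

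*Protocol*

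**What the plan says.** The substudy's primary endpoint in Table 12 (Protocol Section 12.4) is "Frequency of any SAEs, Protocol Specified AESIs, NOCMCs, and MAAEs from Substudy Day 1 to Substudy Day 366". Section 12.10.1 agrees: "SAEs, Protocol Specified AESIs, MAAEs, and NOCMCs will be collected from Substudy Day 1 through the end of the substudy (Substudy Day 366").

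Section 12.11.8 has a different start. It says the same four classes are "collected from the time of first mRNA-1273 vaccination through 12 months after the third mRNA-1273 vaccination", and the design description in Section 12.5 uses the same words. Section 12.11.6 sends the reader to Section 12.11.8 for the analysis of the primary endpoint.

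On reporting, Section 12.11.8 says: "The numbers of SAEs and MAAEs will be reported by detailed listings showing the event description", along with "relevant dates (vaccinations and AEs), severity, relatedness, and outcome for each event". It adds that "the proportion of subjects and exact 95% CIs of AEs in aggregate and by MedDRA categories will be computed". It gives no reporting format for Protocol Specified AESIs or NOCMCs.

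The population comes from Section 12.11.3: "The Safety Analysis population includes all subjects who received the third mRNA-1273 vaccination". The third dose is "given six to twelve months after receipt of their second vaccination in the main study" (Section 12.1).

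**The concern.** The substudy asks how safe a third 100 mcg dose is. Every member of its safety population already has months of main-study follow-up. An event during those months cannot have been caused by a dose not yet given, yet the section named as the primary analysis describes a window that includes it.

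The main study has a partial safeguard. Section 9.3 plans a modified safety analysis that leaves out data collected after the third dose. Appendix A has no matching rule that leaves out data from before it.

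The added time need not be equal across cohorts. Section 12.5 offers the third dose to the 25 and 50 mcg cohorts as early as practicable once the Day 209 visit is done. The 100 and 250 mcg cohorts are to be offered it by the end of the Day 394 visit window. A by-cohort display using the longer window could therefore mix original dose with length of observation.

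**Working it through.** **The plan's own substudy figures.** Section 12.11.2 gives two probabilities of seeing at least one AE, each from 1 − (1 − p)^n:

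- n = 5, p = 0.20: 1 − 0.80^5 = 0.672 (stated as about 67%).
- n = 120, p = 0.03: 1 − 0.97^120 = 0.974 (stated as about 97%).

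Both reproduce. Neither depends on the event window, so they do not settle this point.

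**The four statements side by side.**

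| Place in Appendix A | Role | Start | End |
|---|---|---|---|
| Table 12 | Primary endpoint | Substudy Day 1 | Substudy Day 366 |
| 12.10.1 | AE reporting | Substudy Day 1 | Substudy Day 366 |
| 12.5 | Design | First vaccination, main study | 12 months after third dose |
| 12.11.8 | Safety analysis | First vaccination, main study | 12 months after third dose |

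The end points agree and the starts do not.

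**Length of each window.** Inputs:

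- Endpoint window: Substudy Day 1 to Day 366 is 365 days.
- Earliest third dose: main-study Day 209 (Visit 13), because Section 12.5 has subjects leave the main schedule between Visit 13 and the close of the Visit 14 window.
- Latest third dose: Day 394 + 14 = Day 408.

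For a third dose on main-study Day d, the time before it is d − 1 days, the total is (d − 1) + 365, the ratio is total / 365, and the share before the third dose is (d − 1) / total.

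| Third dose on | Days before it | Total days | Ratio to 365 | Share before third dose |
|---|---|---|---|---|
| Day 209 | 208 | 573 | 1.57 | 36% |
| Day 394 | 393 | 758 | 2.08 | 52% |
| Day 408 | 407 | 772 | 2.12 | 53% |

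These are nominal days. If Visit 13 falls at the early edge of its 7-day window (Day 202), the first row becomes 201 days before the dose, 566 in total, and a ratio of 1.55.

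**Which outputs are exposed.**

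- SAEs and MAAEs: the numbers and listings have no window other than the sentence in dispute.
- AESIs and NOCMCs: both are in the primary endpoint, but with no stated format nothing shows how or over what period they are summarised.
- The aggregate AE proportion: possibly. It follows the summary of non-serious unsolicited AEs, which runs from the third dose through 28 days, but its own window is not stated.

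**The case against.** The strongest reply is that Section 12.11.8 says collected, not counted. Collection from the first vaccination is literally true: the main study gathers these classes from Day 1 and the substudy carries on. On this reading Table 12 sets what is counted, Section 12.10.1 agrees, and the longer window only describes continuous follow-up. This reply has force, and it is why earlier events could be counted rather than would be. It does not remove the problem. The sentence is the only window the designated analysis section gives for these classes. In the main study's parallel Section 9.4.4, the same kind of sentence matches the endpoint window of Day 1 to Day 394. Section 12.11.8 also starts non-serious unsolicited AEs at the third dose, so it does distinguish the two starting points.

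A reader might infer that the reported MAAE or SAE percentage will be inflated by a factor of 1.6 to 2.1. The documents do not support that. SAEs and MAAEs go into listings that carry vaccination and event dates, so a reader can separate them, and no percentage for either class is specified. The documents give no event rate for this trial; the MAAE frequencies they quote (9.7% and 9.0%) are from the Phase 3 trial. A constant rate is also doubtful, because Section 12.6.2 excludes people with certain earlier events, including a related SAE. Section 12.2 reports no SAEs up to the time of writing.

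A reader might also infer double-counting between the two reports. Section 12.11.4 makes the substudy report an addendum to the main clinical study report, and no pooled total is planned. The same dated event could appear in both, but that is not clearly double-counting.

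Finally, Section 12.11.4 defers detail to a full SAP before the final data lock. The SAP supplied covers only the two-dose study, so it neither settles nor contradicts the point. The substudy is descriptive (Section 12.11.1), so no test is affected.

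**Conclusion.** The inconsistency is real and lies between the substudy's primary endpoint and the section named as its analysis. Followed literally, Section 12.11.8 could add 208 to 407 days from before the third dose to a 365-day window, so that 36% to 53% of the observation period would precede the dose under study. Those lengths rest on nominal visit days and on the third dose falling between Day 209 and Day 408. They measure observation time, not event frequency; the effect on frequencies cannot be quantified from the documents. Whether the extra time actually differs between cohorts depends on when third doses were given within the two offer periods. The wording should be corrected, because it concerns the primary endpoint and leaves the counting rule to whoever programs the tables.

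**What to change.** In Section 12.11.8, and in the substudy SAP, state that substudy summaries and counts of SAEs, Protocol Specified AESIs, MAAEs and NOCMCs include only events with onset from the third vaccination (Substudy Day 1) through Substudy Day 366, as in Table 12. State that earlier events are reported as main-study events or flagged separately in listings. In the same edit, give a reporting format for AESIs and NOCMCs and a window for the aggregate AE proportion.

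The sentence in Section 12.5 may stay if it is labelled as describing collection across the main study and substudy together.

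The cost is a few sentences. Data collection and the figures in Section 12.11.2 do not change.

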### **12.11.9 Baseline Descriptive Statistics**

Summaries of demographic variables such as age, sex, ethnicity, and race will be presented by cohort and overall. Summaries of baseline clinical laboratory values will be presented by cohort and overall.

### **12.11.10 Planned Interim and Early Analyses**

Data may be disseminated to public health officials and partners as needed and included in publications and presentations to inform the global scientific community.

Cumulative safety information, study status, and primary endpoint results may be published, presented at a public forum, or presented as summaries aggregated by study arm at the discretion of the sponsor while the main study is ongoing. Any ad-hoc analyses, jointly developed by the SDCC and/or the VRC, other participating laboratories and ModernaTX, Inc., will be executed by the SDCC as needed. None of the interim analyses will include any formal statistical hypothesis testing; therefore, p value adjustment will not be made to any analyses.

#### **12.11.10.1 Interim Safety Analyses**

Given the need for rapid review and dissemination of study data for public health reasons, AEs and SAEs may be reviewed as necessary outside of SMC reviews. The SMC will not need to meet (unless halting rules are met), and materials will be provided electronically. Documentation of review and any concerns noted will be solicited electronically.

#### **12.11.10.2 Interim Immunogenicity Review**

For public health reasons there may be several immunogenicity reviews as needed.

Data may be disseminated to public health officials and partners as needed and included in publications and presentations to inform the global scientific community.

#### **12.11.10.3 Interim Immunogenicity and Safety Review**

Interim analyses of safety, reactogenicity, and immunologic response data may be done, as needed.

### **12.11.11 Sub-Group Analyses**

The protocol does not define any formal subgroup analyses, and the substudy is not adequately powered to perform subgroup analyses.

### **12.11.12 Tabulation of Individual Subject Data**

In general, all data will be listed, sorted by cohort and subject, and when appropriate by substudy visit number within subject.

### **12.11.13 Exploratory Analyses**

Summaries and analysis of immunogenicity data will be presented for the mITT population. If there are protocol deviations which may affect the analysis, a PP analysis may also be performed.

GMFR and seroconversion analyses will be done using two definitions of baseline. Baseline 1 will be considered Main Study Day 1 prior to the first mRNA-1273 vaccination (pre-first mRNA-1273 dose baseline) and baseline 2 will be considered Substudy Day 1 prior to the third mRNA-1273 vaccination (pre-third mRNA-1273 dose baseline).

Seroconversion is defined as a 4-fold increase in antibody titer over baseline.

Seroconversion rates, GMFR and GMT for SARS-CoV-2 as measured by IgG ELISA, neutralization assay using SARS-CoV-2 pseudovirus, neutralization assay using live SARS-CoV-2, and multiplex assay IgG ELISA to the SARS-CoV-2 S proteins and SARS-CoV-2 N protein will be calculated for all post third mRNA-1273 timepoints by cohort and will be summarized graphically. Seroconversion rates, GMFR and GMT will be presented with their corresponding 95% CI estimates at each post-vaccination timepoint and overall peak GMT.

Summaries and analysis of cellular assay data will be presented for the mITT population. If there are protocol deviations which may affect the analysis, a PP analysis may also be performed.

The magnitude, phenotype and percentage of cytokine producing S protein-specific T cells will be summarized at each post-vaccination timepoint by vaccination group.

## **12.12 Regulatory, Ethical, and Study Oversight Considerations**

Informed consent for the substudy will be obtained in accordance with [Section 10.1.1](#).

As per [Section 10.1.1.2](#), the rights and privacy of human subjects who participate in genomic or phenotypic research studies will be protected at all times.

If subjects choose not to provide permission for extra blood and secondary research use, they will not be eligible for participation in the optional third mRNA-1273 vaccination substudy.

Subjects may withdraw permission to use substudy samples for secondary use at any time. They will need to contact the participating site and the samples will be removed from the study repository after this substudy is completed and documentation will be completed that outlines the reason for withdrawal of permission for secondary use of samples. Subjects who withdraw consent before the last substudy visit will not have the extra blood drawn for secondary use.

APPENDIX 2. FIGURE MOCK-UPS176
APPENDIX 3. LISTINGS MOCK-UPS.....216

LIST OF ABBREVIATIONS

AE	Adverse Event
ALT	Alanine Aminotransferase
AST	Aspartate Aminotransferase
AUC	Area Under the Curve
BP	Blood Pressure
C	Celsius
CI	Confidence Interval
CRF	Case Report Form
DMID	Division of Microbiology and Infectious Diseases
EDC	Electronic Data Capture
ELISA	Enzyme-linked Immunosorbent Assay
F	Fahrenheit
FRNT	Focus Reduction Neutralization Test
GMT	Geometric Mean Titer
GMFR	Geometric Mean Fold Rise
ICH	International Council on Harmonisation
IRB	Institutional Review Board
LLN	Lower Limit of Normal
µg	Microgram
MedDRA	Medical Dictionary for Regulatory Activities
N	Number (typically refers to subjects)
NIH	National Institutes of Health
PI	Principal Investigator
PP	Per Protocol
PT	Preferred Term
RBC	Red Blood Cell
S-2P	S Protein in its Prefusion Conformation
SAE	Serious Adverse Event
SD	Standard Deviation
SDCC	Statistical and Data Coordinating Center
SMC	Safety Monitoring Committee

SOC	System Organ Class
SOP	Standard Operating Procedures
ULN	Upper Limit of Normal
WBC	White Blood Cell
WHO	World Health Organization

1. PREFACE

The Statistical Analysis Plan (SAP) for “Phase I, Open-Label, Dose-Ranging Study of the Safety and Immunogenicity of 2019-nCoV Vaccine (mRNA-1273) in Healthy Adults” (DMID Protocol 20-0003) describes and expands upon the statistical information presented in the protocol. This document describes all planned analyses and provides reasons and justifications for these analyses. It also includes sample tables, listings, and figures planned for the final analyses. Regarding the final analyses and Clinical Study Report (CSR), this SAP follows the International Conference on Harmonisation of Technical Requirements for Registration of Pharmaceuticals for Human Use (ICH) Guidelines, as indicated in Topic E3 (Structure and Content of Clinical Study Reports), and more generally is consistent with Topic E8 (General Considerations for Clinical Trials) and Topic E9 (Statistical Principles for Clinical Trials). The structure and content of the SAP provides sufficient detail to meet the requirements identified by the FDA and ICH, while all work planned and reported for this SAP will follow internationally accepted guidelines published by the American Statistical Association and the Royal Statistical Society for statistical practice.

This document contains a review of the study design, general statistical considerations, comprehensive statistical analysis methods for immunogenicity and safety outcomes, and a list of proposed tables and figures. Within the table, figure, and listing mock-ups ([Appendix 1](#), [Appendix 2](#), and [Appendix 3](#)), references to CSR sections are included. The reader of this SAP is encouraged to also review the study protocol for details on conduct of the study and the operational aspects of clinical assessments.

